### 7.1 DEMOGRAPHIC AND OTHER BASELINE CHARACTERISTICS

Only descriptive statistics are planned for this section of the report. COPD background characteristics will be summarized.

Body plethysmography will be analyzed descriptively for visit 2.

### 7.2 CONCOMITANT DISEASES AND MEDICATION

Only descriptive statistics are planned for this section of the report. A table of number (%) of patients with concomitant diagnoses (CDs) by system organ class (SOC) and preferred term (PT) will be included along with a supporting listing. Concomitant diagnoses will be coded with the most recent version of the Medical Dictionary for Regulatory Activities (MedDRA) in effect at database lock.

Frequency tables (%) will be presented for medical history and COPD background characteristics.

Pulmonary medication will be summarized as the number (%) of patients taking pulmonary medications within the last three months before visit 1 and during the treatment periods.

### 7.3 TREATMENT COMPLIANCE

Only descriptive statistics are planned for this section of the report. Summary statistics will be given for percent compliance along with the number (%) of patients with compliance in the categories <80% or >120%, 80% - 120%.

### 7.4 PRIMARY ENDPOINT(S)

The primary endpoint is change from baseline in FEV1 AUC0-3h after 4 weeks of treatment.

Analyses will be performed in PIFR optimal ( $\geq 60$  L/min) group and PIFR sub-optimal ( $< 60$  L/min) group separately.

#### 7.4.1 Primary analysis of the primary endpoint(s)

The primary endpoint will be analyzed using an ANCOVA model including the fixed, categorical effect of treatment and the fixed continuous effect of baseline. The data is collected at baseline (visit 2) and at visit 4.

Significance tests will be based on adjusted means using a two-sided  $\alpha = 0.05$  (two-sided 95% confidence intervals).

The primary analysis will be performed on the FAS within the optimal and sub-optimal PIFR groups, respectively. Patients will be analyzed according to the PIFR stratum to which they belong (regardless of any miss-assignment to treatment based on identification of the wrong stratum), as such an error occurs before randomization and is therefore consistent with regulatory guidance.

The Kenward-Roger approximation will be used to estimate denominator degrees of freedom and adjust standard errors. Significance tests will be based on least-squares means using a two-sided  $\alpha = 0.05$  (two-sided 95% confidence intervals).

The following SAS code will be used for the analysis.

```
PROC MIXED DATA=alldat method=reml order=formatted;
  CLASS trtp (ref=last);
  MODEL chg = base trtp ;
  LSMEANS trtp / cl diff om cov;
RUN;
```

Here the endpoint is chg (change from baseline), baseline value of the endpoint is base and the treatment group is trtp. The data set alldat will be set to the optimal and sub-optimal PIFR subgroups, respectively. The data set should only include post baseline visits since change from baseline will be identical to zero for the baseline visit.

#### 7.4.2 Sensitivity analysis, subgroup analysis, exploratory analysis of the primary endpoint(s)

##### Sensitivity analysis

Additional models will include covariates such as severity (e.g. GOLD stage), gender and age. These models will be analyzed separately for each PIFR subgroup.

##### Missing data analysis

The ANCOVA primary analysis only accounts for missing observations under the MCAR (missing completely at random) assumption. The robustness of the primary analysis to the

MAR (missing at random) assumption will therefore be assessed by performing a multiple imputation (MI) sensitivity analysis with an extended covariate set. Data from Trough FEV1 will also be included in the imputation procedure as it is measured at both visits 3 and 4. It therefore may provide information about patient state prior to discontinuation that is not available directly for the primary endpoint and hence reduce any biases caused by missing data.

Missing data will be multiply imputed 100 times using the MCMC (Markov Chain Monte Carlo) method. The imputation will be performed separately for each combination of treatment and PIFR subgroup. Separate chains will be used for each imputation, with 1000 burn-in iterations. Jeffrey's prior will be used. The seed number will be set to 123795. The following variables will be included in the multiple imputation model: treatment (Tio+Olo vs placebo), continuous baseline FEV1, continuous age, gender (male or female) and disease severity (GOLD group 2 or 3), smoking (yes/no), previous exacerbation (yes/no), country (US, Germany), change from baseline Trough FEV1 at visit 3 and 4 and change from baseline FEV1 AUC0-3h at visit 4.

For each imputed complete data set, the primary endpoint will be analyzed at visit 4 using the primary ANCOVA analysis model. The 100 estimates and standard errors will then be combined using Rubin's rules (16,17) to produce a single estimate with standard error, confidence interval and nominal p-value.

The following SAS code will be used for multiple imputation step.

```
PROC MI data=midat seed=123795 n impute=100 out=miout;
  VAR var;
  MCMC chain=multiple nbiter=1000 prior=jeffreys;
  BY pifr trtp;
RUN;
```

Here the data set is midat, var are all the variables to be entered into model, trtp is the treatment group and pifr is the PIFR sub group. The data set midat must have one record per patient with all variables for each visit arranged horizontally. The variable chg4 is the change from baseline for the endpoint of interest to be analyzed below.

An ANCOVA model will be used on the result of the imputations using the SAS code as follows.

```
PROC SORT data=miout;
  BY _imputation_ pifr;
RUN;
```

```
ODS OUTPUT diff= mixdiff ;
ODS LISTING CLOSE;
```

```
PROC MIXED DATA=miout method=reml order=formatted;
```

```
BY _imputation_ pifr;  
CLASS trtp (ref=last);  
MODEL chg4 = trtp var / solution cl covb ddfm=KR s;  
LSMEANS trtp / cl diff om cov;  
RUN;
```

ODS LISTING;

Finally the results of the 100 ANCOVA analyses will be combined using the SAS code below.

```
PROC SORT data=mixdiff ;  
  BY pifr _imputation_;  
RUN;
```

```
PROC MIANALYZE data=mixdiff;  
  BY pifr;  
  MODELEFFECTS estimate;  
  STDERR stderr;  
run;
```

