7.4 HANDLING OF MISSING DATA

Missing completely at random is assumed for the primary endpoint as very little missing data is expected and no imputation will be performed. The REML-based MMRM model described in [section 7.3.2](#) will handle missing data due to early drop outs or missing data in between visits which are assumed to be missing at random. Additional details on the imputation of missing data will be specified in the TSAP prior to unblinding.

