7.6 DETERMINATION OF SAMPLE SIZE

From previous studies, an appropriate estimate of the standard deviation (SD) for change from baseline in $\text{FEV}_1 \text{ AUC}_{0-3h}$ ($\Delta \text{FEV}_1 \text{ AUC}_{0-3h}$) and trough FEV_1 (ΔTFEV_1) is 210 mL ([c02098902-03](#), [c02037872-05](#)). Based on an assumed treatment difference of 260 ml in $\Delta \text{FEV}_1 \text{ AUC}_{0-3h}$ and 140 ml in ΔTFEV_1 between tiotropium + olodaterol Respimat® and placebo Respimat®, two-sided alpha of 0.05 and SD of 210 ml, a total of 98 patients will provide 99% power within the optimal and sub-optimal PIFR subpopulations for FEV_1 , AUC_{0-3h} and 90% power for trough FEV_1 . The results of power calculations are shown in Tables 7.6: 1 and [7.6: 2](#). From previous studies ([c02098902-03](#), [c02037872-05](#)), the discontinuation rate is assumed to be low within the first 2-4 weeks.

Therefore, a sample size of 200 patients overall with 1:1 randomization ratio and 100 within each subpopulation (100 in optimal PIFR and 100 in sub-optimal PIFR) will provide adequate power to detect a treatment difference of 260 ml for $\text{FEV}_1 \text{ AUC}_{0-3h}$ and to detect a treatment difference of 140 ml for trough FEV_1 .

Table 7.6: 1 Sample size to achieve 90% power assuming two-sided alpha=0.05 and standard deviation of 210 ml

Power	Difference in ΔTFEV_1	SD	N Total
90%	120 ml	210 ml	132
90%	130 ml	210 ml	112
90%	140 ml	210 ml	98
90%	150 ml	210 ml	86
90%	160 ml	210 ml	76
Power	Difference in $\Delta \text{FEV}_1 \text{ AUC}_{0-3h}$	SD	N Total
90%	260 ml	210 ml	30
90%	280 ml	210 ml	26
90%	300 ml	210 ml	24

Proprietary confidential information © 2020 Boehringer Ingelheim International GmbH or one or more of its affiliated companies

Table 7.6: 2 Power for given sample size of 98 patients assuming a two-sided alpha=0.05 and standard deviation of 210 ml

Difference in ΔTFEV_1	SD	N Total	Power
120 ml	210 ml	98	80%
130 ml	210 ml	98	86%
140 ml	210 ml	98	90%
Difference in $\Delta\text{FEV1 AUC}_{0-3h}$	SD	N Total	Power
260 ml	210 ml	98	>99%
280 ml	210 ml	98	>99%
300 ml	210 ml	98	>99%

Calculations were performed using SAS PROC POWER in SAS v9.4.

8. INFORMED CONSENT, TRIAL RECORDS, DATA PROTECTION, PUBLICATION POLICY, AND ADMINISTRATIVE STRUCTURE

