##### **Missing data analysis**

A multiple imputation analysis will be performed on the key secondary endpoint similar to that of the primary endpoint described in section 7.4.2.

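### The multiple imputation said to assess robustness to MAR is itself a MAR analysis; outside one fixed worst-observation rule no visible analysis examines departures from MAR, and the pooling code omits the complete-data degrees of freedom

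*SAP*

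**What the plan says.** Protocol 7.4 sets the assumption for the primary endpoint: "Missing completely at random is assumed for the primary endpoint as very little missing data is expected and no imputation will be performed". It assumes missing at random for the MMRM of trough FEV1.

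SAP 7.4.2 repeats that the ANCOVA is valid only under MCAR. It then says that robustness to the "MAR (missing at random) assumption will therefore be assessed by performing a multiple imputation (MI) sensitivity analysis with an extended covariate set". The imputation uses MCMC with 100 datasets and is run separately for each arm within each PIFR group. Its variables include age, gender, GOLD group, smoking, previous exacerbation, country, trough FEV1 change at Visits 3 and 4, and AUC0-3h change at Visit 4. No shift, reference-based or tipping-point step follows.

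For trough FEV1, SAP 7.5.1.2 says: "A multiple imputation analysis will be performed on the key secondary endpoint similar to that of the primary endpoint described in section 7.4.2".

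SAP 6.6 contains three further elements:
- It calls the sensitivity analysis an 'adjusted' multiple imputation and refers to 7.4.1 and 7.5.1.2 for details. Neither these sections nor 7.4.2 defines an adjustment.
- When a patient discontinues because of an adverse event indicative of worsening COPD, missing visits take the patient's worst earlier observation.
- Data from visits more than one day after stopping study medication are not used.

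The pooling step is "PROC MIANALYZE data=mixdiff" with BY, MODELEFFECTS and STDERR statements only.

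**The concern.** A sensitivity analysis for an assumption has to relax or vary that assumption. Imputation within arm draws a missing active-arm value from the distribution of observed active-arm patients with similar recorded data, and that is the MAR assumption. If the ANCOVA and the imputation agree, the reader learns that moving from MCAR to MAR changes little. The reader learns nothing about patients who left because they were doing worse than their recorded data suggest.

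Such dropout is plausible here. The protocol has patients discontinue for medical reasons, for interfering concomitant medication or by choice (3.3.4.1), and SAP 6.6 then discards data collected later. AUC0-3h is not measured at Visit 3, so for the primary endpoint an early dropout contributes at most trough data to the imputation.

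The second issue is technical. The per-imputation model requests Kenward-Roger degrees of freedom, so finite-sample inference is intended. Without EDF=, the pooling treats the complete-data degrees of freedom as infinite, although each PIFR stratum has about 100 patients.

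**Working it through.** **Inputs.** Protocol 7.6: "two-sided alpha of 0.05 and SD of 210 ml, a total of 98 patients will provide 99% power" (90% for trough FEV1); planned differences 260 mL (AUC0-3h) and 140 mL (trough); "a sample size of 200 patients overall with 1:1 randomization ratio and 100 within each subpopulation", hence 50 per arm per stratum. SAP 7.4.2: m = 100. No dropout rate is given, only that it is assumed low, so the missing fractions below are assumptions.

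**The plan's own figure.** Two-sample t-test power (noncentral t) at N = 98 is 90.4% for 140 mL and above 99.9% for 260 mL. All eight N values in Table 7.6:1 reproduce. At N = 100 the trough power is 91.0%.

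**What each analysis assumes**

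| Analysis | Assumption about missing values |
|---|---|
| Primary ANCOVA | MCAR |
| MI for AUC0-3h | MAR given the extended variable list |
| MMRM for trough | MAR given treatment, baseline and the other visit |
| MI for trough | MAR given the extended variable list |
| Worst-observation rule (SAP 6.6) | Not MAR; fixed; COPD-worsening AE discontinuations only |
| Models adding severity, gender, age | Do not address missing data |

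No row varies MAR.

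**How large a departure would matter.** Suppose a fraction f is missing in each arm and imputed active-arm values are lowered by delta. The estimate falls by f × delta. With SE = 210 × √(2 / (50(1 − f))) and t = 1.985 (97 df), significance is lost at delta = (D − t × SE) / f.

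Example: trough, D = 140, f = 0.10. SE = 210 × √(2/45) = 44.3; boundary 1.985 × 44.3 = 87.9; delta = (140 − 87.9)/0.10 ≈ 521 mL.

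| f | Boundary (mL) | Delta, trough at 140 | Delta, AUC0-3h at 260 |
|---|---|---|---|
| 5% | 85.5 | 1,090 | 3,490 |
| 10% | 87.9 | 521 | 1,721 |
| 20% | 93.2 | 234 | 834 |

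If the observed trough difference is only 100 mL, the delta is (100 − 87.9)/0.10 ≈ 120 mL with 5 missing per arm. With 2 missing per arm (f = 0.04, boundary 85.1) it is about 372 mL. If the true difference is 140 mL and 5 per arm are missing, the chance of a significant result at or below 100 mL is Φ((100 − 140)/44.3) − Φ((87.9 − 140)/44.3) ≈ 6% per stratum.

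**Pooling degrees of freedom.** Let g be the fraction of missing information.
- Without EDF=: (m − 1)(1 + 1/r)² with r = g/(1 − g), which equals 99/g². At g = 0.05 this is 39,600, t = 1.960.
- Barnard-Rubin with complete-data df ν₀ = 97: ν_obs = (98/100) × 97 × 0.95 = 90.3; pooled df = 1/(1/39,600 + 1/90.3) = 90.1, t = 1.987.
- Ratio 1.987/1.960 ≈ 1.014. Coverage of the interval as coded is 94.7%, and a correct p of 0.050 would print as 0.047.
- For g from 1% to 30% and ν₀ of 97, or 89 if eight covariates are added (assumed), the correct interval is 1.3 to 2.0% wider and coverage as coded is 94.5 to 94.7%.

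**The case against.** Several counter-arguments have force.

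- **The sentence can be read as the step from MCAR to MAR.** It follows directly on the statement that the ANCOVA needs MCAR, and the imputation does make that step. On this reading the first fault is loose wording. That stands, but the text as written names MAR as the assumption being assessed.
- **Exacerbation dropout is already handled.** A reader might infer that the protocol's discontinuation for exacerbation leaves lung-function-related dropout untreated. The documents do not support this: the worst-observation rule covers discontinuations due to adverse events grouped as COPD exacerbation or lower respiratory disorders. A similar within-visit rule applies after rescue use at Visits 2 and 4. These rules are fixed and never varied, so the open question concerns the other dropouts.
- **The imputation is not redundant for trough FEV1.** A reader might infer that it adds nothing to the MMRM. That is too strong: it conditions on more covariates and on AUC0-3h, and is fitted separately by arm. Agreement would be informative within MAR, though not about departures from it.
- **The 120 mL case is selected.** It needs 10% missing, an observed effect 40 mL below plan and only about 12 mL above the significance boundary, and a penalty on the active arm alone. It shows where the result would be fragile, not that it is expected to be.
- **The EDF= effect is small** and touches an analysis whose p-value the SAP calls nominal. This stands.
- **Parts of the SAP are redacted or removed**, so the statement can cover only the visible text.

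**Conclusion.** The stated aim and the method do not match. The imputation relaxes MCAR to MAR for AUC0-3h and widens the conditioning set for trough FEV1. Apart from the fixed worst-observation rule, no visible analysis examines departures from MAR, and the 'adjusted' imputation has no defined adjustment.

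The practical size is modest. At the planned effects and low dropout the tipping shifts are implausibly large, most of all for AUC0-3h. The exposed case is trough FEV1 with an observed effect well below 140 mL or with dropout near 20%. It would be wrong to infer that the confirmatory tests are compromised: neither the ANCOVA nor the MMRM uses this imputation, and the EDF= omission affects only the pooled sensitivity intervals and their nominal p-values.

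The figures rest on an SD of 210 mL, 50 per arm, assumed missing fractions, and an approximate standard error taken from observed patients. Priority is low to moderate.

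**What to change.** 1. In SAP 7.4.2, describe the imputation as relaxing MCAR to MAR.
2. Define the 'adjusted' imputation of SAP 6.6 as a delta-adjusted tipping-point step on the same 100 imputed datasets. Lower the imputed Visit 4 values in the T+O arm by 0, 50, 100 mL and so on, rerun the analysis and pooling, and report the delta at which each of the four hypotheses loses significance. State whether values filled by the worst-observation rule are shifted too; if that rule is applied before imputation, a shift of imputed values alone would not reach them. Correct the cross-reference from 7.4.1 to 7.4.2.
3. Add EDF= to PROC MIANALYZE for each PIFR stratum, set to the residual df of the model actually fitted: about 97 for baseline plus treatment, fewer if further covariates stay in. The text calls for the primary ANCOVA model, but the code fits `trtp var`, where `var` also names the imputation list and so includes post-baseline variables. Reconcile the two.

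The cost is SAP wording, a short data step, one option and one more sensitivity table. The confirmatory tests do not change.

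### SAP 7.4.2: the model line run after multiple imputation does not name the baseline term and reuses the imputation placeholder, so the code as defined does not fit the primary ANCOVA that the text calls for

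*SAP*

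**What the plan says.** SAP 7.4.1 defines the primary analysis in words as an ANCOVA with treatment and baseline, and codes it as "MODEL chg = base trtp".

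SAP 7.4.2, under Missing data analysis, adds a "multiple imputation (MI) sensitivity analysis with an extended covariate set". Its prose says that for every completed data set "the primary endpoint will be analyzed at visit 4 using the primary ANCOVA analysis model". Trough FEV1 is brought in for the imputation: "Data from Trough FEV1 will also be included in the imputation procedure as it is measured at both visits 3 and 4". The listed imputation variables are treatment, baseline FEV1, age, gender, GOLD group, smoking, previous exacerbation, country, "change from baseline Trough FEV1 at visit 3 and 4", and the visit 4 change in FEV1 AUC0-3h, which is the primary endpoint itself.

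The PROC MI code uses `VAR var`. The note on that code reads: "Here the data set is midat, var are all the variables to be entered into model". The PROC MIXED code for the analysis step is then "MODEL chg4 = trtp var / solution cl covb ddfm=KR s", where `chg4` is the endpoint being analysed. After it the SAP says: "Finally the results of the 100 ANCOVA analyses will be combined using the SAS code below".

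SAP 6.6 sends the reader to 7.4.1 and 7.5.1.2 for the imputation details. Section 7.4.1 contains no imputation, and 7.5.1.2 says only that the key secondary analysis is similar to 7.4.2.

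**The concern.** The prose and the code for one step do not match on the face of the document. The prose asks for baseline plus treatment. The code asks for treatment plus a placeholder that was last used for the imputation list, and that list contains two post-randomisation measurements and the outcome.

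Putting post-baseline variables in an imputation model is sound and is the stated purpose of including trough FEV1. Putting them in the analysis model is a different matter: trough FEV1 responds to treatment, so adjusting for it removes part of the effect being estimated.

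The analysis exists to show whether the primary result is robust to missing data, because SAP 7.4.2 itself says the primary ANCOVA copes only with data missing completely at random. It is the only missing-data sensitivity analysis set out for the primary endpoint in the visible text. If the wrong covariates entered, the estimate would move for reasons unrelated to missing data, and the gap could be misread as sensitivity to missingness.

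**Working it through.** **Planning inputs (Protocol 7.5 and 7.6).** Difference 260 mL for FEV1 AUC0-3h and 140 mL for trough FEV1, SD 210 mL, two-sided 0.05, about 50 per arm in each PIFR stratum. These inputs reproduce the protocol's figures. With 98 patients the standard error is 210 × √(2/49) = 42.4 mL, so the noncentrality is 140/42.4 = 3.30 for trough and 260/42.4 = 6.13 for AUC. The two-sample t-test then has power 90.4% and above 99.9%, as stated.

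**What each reading of `var` fits in the PROC MIXED step.**

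1. *`var` = `base`.* The model is the primary ANCOVA, so code and prose agree. The expected coefficient is 260 mL, with standard error about 210 × √(2/50) = 42 mL.
2. *`var` = the full imputation list.* `chg4` is on both sides. Its own coefficient is 1 and everything else is 0. In simulation the largest absolute treatment coefficient was about 3 × 10⁻¹² mL. This would be noticed at once.
3. *`var` = the list with only the outcome dropped.* The model adjusts for trough change at visits 3 and 4. It runs without error.
4. *`var` = extra baseline covariates only.* The simulated mean estimate is 260 to 261 mL, so there is no bias, but this is not the model that the prose names.

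**Size under reading 3.** With equal SDs, the expected treatment coefficient is

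d_AUC − (b₃ × d₃ + b₄ × d₄),

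where d₃ and d₄ are the trough effects at visits 3 and 4, and b₃ and b₄ are the within-arm regression slopes of AUC on the two troughs:

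b₃ = (r_A3 − r_A4 × r₃₄)/(1 − r₃₄²) and b₄ = (r_A4 − r_A3 × r₃₄)/(1 − r₃₄²).

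The documents give d_AUC = 260 and d₄ = 140. They give no correlations and no visit 3 effect, so these are assumed: five correlation settings, and d₃ of 100, 140 or 180 mL.

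Worked example, with r_A4 = 0.5, r_A3 = 0.4, r₃₄ = 0.5 and d₃ = 140:
- b₃ = (0.4 − 0.25)/0.75 = 0.20
- b₄ = (0.5 − 0.20)/0.75 = 0.40
- coefficient = 260 − 140 × 0.60 = 176 mL

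| r_A4 / r_A3 / r₃₄ | d₃ = 100 | d₃ = 140 | d₃ = 180 |
|---|---|---|---|
| 0.3 / 0.3 / 0.3 | 204.6 | 195.4 | 186.2 |
| 0.5 / 0.4 / 0.5 | 184.0 | 176.0 | 168.0 |
| 0.7 / 0.6 / 0.7 | 161.6 | 152.9 | 144.3 |
| 0.85 / 0.75 / 0.8 | 143.3 | 135.6 | 127.8 |
| 0.9 / 0.75 / 0.75 | 134.9 | 128.0 | 121.1 |

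The range is 121 to 205 mL, that is (260 − 204.6)/260 = 21% to (260 − 121.1)/260 = 53% below the planning effect, with no data missing.

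A simulation of 4,000 strata per setting (50 per arm, d₃ = 140) agrees, with means of 195.3, 176.7, 153.2, 135.6 and 128.7 mL. It gave p < 0.05 in at least 99% of strata in every setting, so the distortion would be in the estimate and not in significance.

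**The case against.** The best defence is that `var` is plainly schematic. The text list includes treatment, yet PROC MI runs separately by treatment arm, where treatment is constant, and the MODEL line already carries `trtp`. So `var` cannot be the literal list even in the imputation step, and a programmer must substitute names at each step. The prose says which names: it calls for the primary ANCOVA, 7.4.1 defines that model in words and code, and trough FEV1 is assigned to the imputation procedure. No sentence puts it in the analysis model.

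Most of this stands. A reader might infer that the SAP prescribes adjustment for post-randomisation trough FEV1, or that nothing in it settles the model. The documents support neither, because the prose names one model.

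What does not stand is that the code is therefore adequate. To reach `base`, `var` must change meaning between two consecutive steps and stand for a single variable although its definition speaks of all the variables. The phrase about an extended covariate set, and the label of adjusted multiple imputation in SAP 6.6, pull the other way. A programmer who follows the code gets a degenerate fit, and the easiest repair, deleting the outcome from the list, gives reading 3.

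It is also fair that the consequence is small. The p-value is nominal, Protocol 7.4 expects very little missing data for the primary endpoint, and Protocol 7.6 assumes low discontinuation.

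**Conclusion.** The point holds as a defect in a stated analysis line. Taken on the definition given, the code does not fit the model that the text names; it matches only if `var` is silently read as `base`.

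The 121 to 205 mL range is illustrative. It rests on assumed correlations, an assumed visit 3 effect, equal SDs, and a reading that the prose contradicts. It shows the direction and the order of size of an error that the code invites, and should not be quoted as a bias built into the plan.

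The scope is the multiple-imputation sensitivity analysis alone. A reader might infer a threat to the trial's main conclusions; there is none, since the confirmatory ANCOVA, the key secondary MMRM, the test hierarchy and the sample size do not use this line. No size is claimed for the key secondary imputation analysis, because SAP 7.5.1.2 does not state its model.

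It should still be fixed: the correction is trivial, and this analysis is the SAP's answer to the missing-data limitation that it acknowledges in its own primary model.

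**What to change.** In SAP 7.4.2:
- Write the post-imputation line as `MODEL chg4 = base trtp / ddfm=kr`.
- Give the PROC MI variable list its own name, write the list out, and keep the post-baseline variables only there.
- State that the extended covariate set refers to the imputation model. If extra covariates are wanted in the analysis model, name them, restrict them to baseline variables, and present that as a separate model.

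Two editorial points:
- Correct the SAP 6.6 cross-reference from 7.4.1 to 7.4.2.
- State in SAP 7.5.1.2 that the imputed key secondary analysis uses no post-baseline variable as a covariate.

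The cost is one model line, one renamed placeholder, two clarifying sentences and one cross-reference. Data collection and the confirmatory analysis do not change.
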